### **Key Secondary Endpoint**

The key secondary endpoint will be analyzed using a stratified log-rank test with factors for treatment group and the randomization stratification variables. Separate analyses will be carried out for each dose group.

The Statistical Analysis Plan will describe in detail the methods to be used for the primary and key secondary endpoints. The methods will be designed to ensure protection of the Type I error rate across the primary and key secondary endpoints.

#### **8.1.3. Treatment of Subjects Lost to Follow-up**

Several subjects in this trial may undergo significant interventions during the trial and some may die. Specifically, about 10% of subjects are not expected to reach the 12-week time point for reasons such as death, risk of or actual necrotizing enterocolitis (NEC), or other complications. An additional 10% of subjects are not expected to reach the 24 week time point for similar reasons. Partial data collected from such infants are informative for comparing the treatment arms. For subjects who do not provide any data during the 10-day period for the week 12 or week 24 time point, the endpoint will be imputed using multiple imputation, replacing each missing value with a set of plausible values that represent the uncertainty about the correct value to impute. The multiple imputed datasets will then be analyzed by standard statistical procedures for complete data and combining the results from these analyses. Multiple imputation does not attempt to estimate each missing value through simulated values, but rather to present a random sample of the missing values.

Multiple imputation involves three steps:

1. the missing values are filled in  $m$  times to generate  $m$  complete data sets,
2. the  $m$  complete datasets are analyzed using standard statistical procedures,
3. the results from the  $m$  analyses are combined (using a roll-up estimator) for statistical inference.

The SAP will present full details of the methodology.

## **8.2. ANALYSIS SETS**

### **8.2.1. Safety Analysis Set**

The safety analysis set will consist of all subjects for whom the study treatment, whether placebo or NTRA-9620, was initiated.

### **8.2.2. Full Analysis Set**

The Full Analysis Set (FAS) will consist of all randomized subjects. Subjects will be analyzed by randomized treatment.

Blind review will be used to assess which interventions undergone during the trial are likely to affect outcome. As noted in the preceding section, major interventions are expected to be independent of treatment.

### **8.2.3. Modified Intent-to-Treat Set**

The Modified Intent-to-Treat (mITT) set will consist of all randomized subjects who received at least one dose of NTRA-9620 or placebo, and who have baseline and at least one post-baseline measurement on the primary endpoint (for primary endpoint testing) or the key secondary endpoints (for key secondary endpoint testing). Subjects will be analyzed by randomized treatment.

Blind review will be used to assess which interventions undergone during the trial are likely to affect outcome. As noted in the preceding section, major interventions are expected to be independent of treatment.

### **8.2.4. Per-Protocol Analysis Set**

The per-protocol (PP) analysis set will be the subset of FAS subjects with no major protocol violation likely to affect outcome prior to the time point at which a confirmatory endpoint is tested. Blind review will be used to assess which interventions undergone during the trial are likely to affect outcome. Subjects with these major interventions will be included in the PP up to the point of intervention.

Analysis of PP sets need to be performed in a way that adjusts for the selection bias inherent in PP sets. The SAP will describe these analyses.

## **8.3. STUDY ENDPOINTS**

This section presents the safety and efficacy endpoints in this trial. The primary endpoints are computed as percent change from baseline to 12 weeks and to 24 weeks, where the change is based on the average of the daily values obtained during the specified week. The difference between the relevant week and baseline is calculated such that the expected outcomes are positive (i.e., since greater %PN at baseline is expected, the primary endpoint is computed by subtracting the 12-week or 24 week measurement from baseline).

### **8.3.1. Safety Endpoints**

Safety endpoints are SAEs and AEs occurring at any time during the trial or follow-up.

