#### **4.1.13. Adverse Events (AEs)**

The information obtained during study visits, physical examinations, vital signs measurements, blood testing, and by any other means will be evaluated in light of baseline medical data and thus provide the basis for identification and grading of AEs.

The AEs reported during the trial will be graded (see Section [7.1](#)), documented, and assessed in light of their clinical significance and relation to investigational product. In addition, the following information regarding the AE must be obtained and recorded in subject's source document and Case Report Form (CRF): AE description, start date, end date (if applicable) or ongoing, severity, seriousness, investigator's assessment of the relationship of the AE to study drug, outcome (i.e., resolved, resolved with sequelae, ongoing, death due to this AE, death due to other events, unknown) and action taken (e.g., concomitant medication). Information regarding occurrence of AE monitoring will be captured throughout the study, from Day 7 (initiation of dosing) 28 days after the final primary study visit at Week 28 (Day 196). AEs considered treatment related by the Investigator will be documented after the primary study completion on Week 52 (Day 364) and Week 104 (Day 728) to assess any potentially related adverse outcomes of treatment and re-hospitalizations. Pre-treatment emergent events will not be considered as AEs, but will be recorded as medical history.

Prior to this current trial, four clinical trials including three in preterm infants and one in SBS infant subjects have been performed with oral administration of insulin. No treatment-related adverse events have been reported and no systemic absorption of insulin has been detected.

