**Table 1: Adverse Events Observed in Previous Nutrinia Clinical Studies of Oral Insulin in Premature Infants**

According to the study investigator, none of the recorded adverse events was related to the investigational product or trial.

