#### **8.5.4. Safety Analysis**

The safety analyses will be descriptive and narrative in nature, with SAEs and AEs coded using MedDRA and tabulated by body system, preferred term, treatment group, severity and relation to procedure. Descriptive statistics will be provided by treatment group as appropriate.

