- o. All concomitant medication given within 30 days prior to the time of consent through the Week 28 assessment. After week 28, only clinically significant medications that are used to treat potential adverse effects of NTRA-9620 will be recorded.
- p. AE monitoring will be conducted throughout the study from Day 0 (initiation of dosing) until 28 days after the final primary study visit at Week 28 (Day 196). AEs considered to be treatment related by the Investigator will be documented at the post primary study completion on Week 52 (Days 364) and Week 104 (Day 728) to assess any potentially related adverse outcomes of treatment. Pre-treatment emergent events will be recorded on the medical history.
- q. The total amount of parenteral nutrition administered for each feeding will be recorded in each study visit. The volume and caloric value of parenteral feeding will be entered into each study visit.
- r. The total amount of enteral nutrition administered for each feeding during the day will be recorded. The volume and caloric value of enteral feeding will be entered into each study visit.

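### The protocol contradicts itself on which adverse events are recorded after the primary study, so the all-events safety endpoint of Section 8.3.1 is not assured for up to 76 of 104 weeks

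*Combined protocol and SAP*

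**What the plan says.** Section 8.3.1 sets the safety endpoint as "SAEs and AEs occurring at any time during the trial or follow-up", with no limit by attribution or date. Several sections govern what is collected after Week 28.

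- **No relatedness filter.** The synopsis visit schedule and Section 4.1.12 include adverse events and re-hospitalizations in the Week 52 and Week 104 visits. Section 4.2.8 and Appendix B footnote c do the same for routine-care visits, if these take place.
- **Related events only.** Section 4.1.13 says that "AEs considered treatment related by the Investigator will be documented after the primary study completion". Footnote p has the same rule: "AEs considered to be treatment related by the Investigator will be documented at the post primary study completion on Week 52". Footnote a and Section 7.1.1 also describe the long-term evaluations in terms of potentially related outcomes.
- **Serious events.** Section 7.2.1 requires all SAEs to be reported, within 24 hours if related and 48 hours if not, and states no end date. Section 7.1.1 has SAEs of either kind followed to resolution, even past a reporting period that it does not define.
- **End of full collection.** Section 7.1.1 ends it at the Week 28 visit (Day 196). Footnote p extends it to "28 days after the final primary study visit at Week 28 (Day 196"), and Section 4.1.13 gives the same later limit.
- **Tabulation.** Section 8.5.4 and the synopsis tabulate events by "severity and relation to procedure". Sections 4.1.13 and 7.1.1 have the investigator record the relationship to study drug.

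**The concern.** An endpoint that counts every event needs a collection rule that captures every event. Here a site working from Section 4.1.12 and a site working from Section 4.1.13 would send different data for the same infant, and the analyst could not tell an absent event from an unrecorded one.

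The related-only rule also weakens what follow-up to Week 104 is for. Counting all events by randomized arm can show an excess that nobody suspected. A list that depends on blinded attribution contains only what someone already suspected. Section 7.1.1 treats an event judged unlikely to be caused by the drug as not related, and Appendix E lists many conditions as expected in this population, so such a judgement would be easy to reach. Section 8.1 leaves analysis detail to a later SAP, but no SAP can restore events that were never entered.

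**Working it through.** **Inputs.** Week 28 is Day 196, Week 52 is Day 364 and Week 104 is Day 728 (Appendix B). The synopsis gives 28 weeks of primary study and 76 weeks of long-term follow-up.

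**The plan's own figure.** 28 + 76 = 104 weeks, and 728 / 7 = 104. The stated follow-up length reproduces.

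**Length of the affected period.**
- Full collection to Day 196 (Section 7.1.1): 728 − 196 = 532 days; 532 / 7 = 76 weeks; 76 / 104 = 73%.
- Full collection to 196 + 28 = Day 224, i.e. Week 32 (Section 4.1.13, footnote p): 728 − 224 = 504 days; 504 / 7 = 72 weeks; 72 / 104 = 69%.
- The two versions differ by 28 days, or 4 weeks.

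**What each text does with a new event in that period.**

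| New event | 8.3.1 endpoint | 4.1.12 visit content | 4.1.13 and footnote p | 7.2.1 SAE reporting |
|---|---|---|---|---|
| Non-serious, judged related | counted | recorded | recorded | not applicable |
| Non-serious, judged unrelated, after Day 224 | counted | recorded | not recorded | not applicable |
| Non-serious, judged unrelated, Day 196 to Day 224 | counted | no visit scheduled | recorded (but not under 7.1.1) | not applicable |
| Serious, judged unrelated, after Day 224 | counted | recorded | not recorded as an AE | reported, if the duty still runs |
| Re-hospitalization | counted if an AE or SAE | recorded as its own item | named in 4.1.13, not in footnote p | hospitalization is an SAE criterion (7.2) |

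The second row is a direct contradiction: the endpoint needs the event and the specific AE rule leaves it out. The fourth row is an ambiguity. Section 7.2.1 would capture the event, but nothing says that its reporting duty for new unrelated SAEs lasts to Week 104.

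**Attribution wording.** The causality categories in Section 7.1.1 (unlikely, possible, probable) all refer to the study drug. No category for relation to a procedure is defined, so the table planned in Section 8.5.4 has no matching field.

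**The case against.** The strongest reply is that the protocol, read as a whole, does collect late serious events. Section 7.2.1 covers all SAEs and sets a separate clock for unrelated ones. Section 7.2 places SAEs within the course of the investigation, and the synopsis gives the study a total length of 104 weeks. Death and hospitalization are SAE criteria. Re-hospitalizations are listed at both late visits, and Section 4.1.12 adds telephone calls every three months. The related-only sentences speak of AEs and do not cancel the SAE duty. Restricting late non-serious events to related ones is a legitimate choice, the safety analysis is descriptive, and the DSMB compares event rates unblinded.

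Much of this stands. A reader might infer from Section 4.1.13 that nothing but related events will be documented after Week 28. The documents do not support that, given Sections 4.1.12, 4.2.8 and 7.2.1.

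The reply does not remove the conflict. Section 4.1.12 lists visit content, whereas Section 4.1.13 and footnote p are the specific AE rules, and they filter. Routine visits under Section 4.2.8 may not happen, and their absence is not treated as missing data. Section 7.2.1 has no end date. A descriptive analysis and a DSMB review both still depend on complete counts by arm. If the restriction on non-serious events is intended, Section 8.3.1 does not reflect it.

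On the tabulation, the AE definition does extend to protocol-imposed interventions, but no attribution to them is recorded.

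**Conclusion.** The protocol is inconsistent on which adverse events are recorded after the primary study and on when full collection ends. The affected period is 76 weeks (73% of 104) if Section 7.1.1 governs and 72 weeks (69%) if Section 4.1.13 and footnote p govern. Where the related-only rule is followed, the Section 8.3.1 endpoint cannot be computed for non-serious AEs, and collection of new unrelated SAEs to Week 104 is not assured. If the unfiltered sections govern and the SAE duty runs to Week 104, the related-only gap closes. The documents do not say which reading applies.

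A reader might go further and expect the long-term safety data to be nearly empty, because Table 1 states that "none of the recorded adverse events was related to the investigational product or trial". The documents do not support that forecast. Section 5.1 introduces Table 1 as a summary of non-drug-related events, so the absence of related ones is built into the table and cannot be used to estimate a related share. Sections 4.1.13 and 5.1 separately report no treatment-related events in four trials, but three of those were in preterm infants, and Section 1.2 describes 24 to 28 days of treatment in preterm infants. No rate is given for late related events, SAEs or re-hospitalizations in this population.

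The tabulation by relation to procedure is a smaller, separate mismatch with the data collected. Neither point touches the efficacy analysis or the sample size.

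**What to change.** 1. Reconcile the synopsis visit schedule, Sections 4.1.12, 4.1.13, 4.2.8, 7.1.1 and 7.2.1, and Appendix B footnotes a, c and p. State one cut-off day for full AE collection.
2. State that all deaths and SAEs are recorded regardless of attribution through Week 104 and tabulated descriptively by arm in the addendum to the study report. Give Section 7.2.1 that end date.
3. For non-serious AEs, either collect all of them through Week 104, or limit Section 8.3.1 to related non-serious AEs after the stated cut-off day.
4. In Section 8.5.4 and the synopsis safety paragraph, replace relation to procedure by relation to study drug.

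The cost is slightly more data entry at the Week 52 and Week 104 visits and the three-monthly calls, all of which are already planned. Narrowing Section 8.3.1 under item 3 adds no data entry for non-serious events, but gives up the comparison of late unrelated ones.

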### 8.3.2. Co-Primary Efficacy Endpoints

The first co-primary endpoints in this trial is percent change in %PN (PC\_PN0-t) from baseline based on caloric intake to 12 weeks and again to 24 weeks. The 12 and 24 week endpoints are calculated as:

$$PC\_PN_{0-t} = 100 * \frac{\%PN_{Baseline} - \%PN_t}{\%PN_{Baseline}}$$

Where

- $t = 12$  or  $24$  weeks
- $\%PN = \%$  Parenteral Nutrition (feeding) will be calculated as parenteral calories divided by total caloric requirements (the Schofield equation (1)).
- PC\_PN0-t observations will be computed as an average over a single week.

Thus, PC\_PN at 12 weeks will be the average of PC\_PN over Days 78 to 84.

PC\_PN at 24 weeks will be the average of PC\_PN over days 162 to 168.

The use of the Schofield equation would be solely in the analysis of the study and would not be used at bedside during the actual trial.

The second co-primary endpoints are responder endpoints, calculated as continuous responder comparisons at 12 weeks and again at 24 weeks. Each test will be carried out at the 1-sided  $p<0.10$  significance level.

### 8.3.3. Key Secondary Endpoint

The trial has the following key secondary endpoint:

Time to reduction of PN to less than 10% of the total caloric intake on each of 14 consecutive days.

### 8.3.4. Other Secondary Endpoints

The study has the following additional secondary endpoints:

- a) Time to wean off  parenteral nutrition
- b) Number of patients achieving readiness to wean off  at 12 and 24 weeks from baseline
- c) Time to 50% PN/IV reduction from baseline in %PN based on total calories.
- d) Time to 50% PN/IV reduction from baseline in %PN based on volume.

 Baseline: prior to treatment. Baseline measurement period should be at least 7 days.

 Wean off defined as complete cessation of parenteral nutrition and achieving full enteral autonomy for two weeks.

 Reduction to PN of less than 10% of the total caloric intake for two weeks.

- e) Number of patients reaching 50% PN/IV reduction from baseline in %PN based on total calories at 12 and 24 weeks
- f) Number of patients reaching 50% PN/IV reduction from baseline in %PN based on volume at 12 and 24 weeks.
- g) Percent change from baseline in %PN/IV based on total calories.
- h) Percent change from baseline in %PN/IV based on volume.
- i) Percent change from baseline in PN/IV fluid volume during treatment period.
- j) Change in Z-scores (Fenton) from baseline during the treatment period.
- k) Percent change from baseline in %EN based on total calories.
- l) Percent change from baseline in %EN based on total volume.
- m) Change from baseline in liver enzymes (ALT, GGT, and total and direct bilirubin).
- n) Change from baseline in plasma citrulline levels.
- o) Change from baseline in body weight during the treatment period.
- p) Weekly average of hours on prescribed PN/IV during the last month of treatment.
- q) General safety variables including episodes of significant feeding intolerance compared to placebo

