#### **3.4.2.2. Secondary Endpoints**

##### **Other Secondary Endpoints**

- a) Time to wean off  parenteral nutrition
- b) Number of patients achieving readiness to wean off  at 12 and 24 weeks from baseline
- c) Time to 50% PN/IV reduction from baseline in %PN based on total calories.
- d) Time to 50% PN/IV reduction from baseline in %PN based on volume.
- e) Number of patients reaching 50% PN/IV reduction from baseline in %PN based on total calories at 12 and 24 weeks
- f) Number of patients reaching 50% PN/IV reduction from baseline in %PN based on volume at 12 and 24 weeks.
- g) Percent change from baseline in %PN/IV based on total calories.
- h) Percent change from baseline in %PN/IV based on volume.
- i) Percent change from baseline in PN/IV fluid volume during treatment period.
- j) Change in Z-scores (Fenton) from baseline during the treatment period.
- k) Percent change from baseline in %EN based on total calories.
- l) Percent change from baseline in %EN based on total volume.
- m) Change from baseline in liver enzymes (ALT, GGT, and total and direct bilirubin).
- n) Change from baseline in plasma citrulline levels.
- o) Change from baseline in body weight during the treatment period.
- p) Weekly average of hours on prescribed PN/IV during the last month of treatment.
- q) General safety variables including episodes of significant feeding intolerance compared to placebo

 Wean off defined as complete cessation of parenteral nutrition and achieving full enteral autonomy for two weeks.

 Reduction to PN of less than 10% of the total caloric intake for 14 consecutive days.

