### 3.4.4. Inclusion Criteria

Subjects must meet *all* of the following criteria to be included:

- 1) Subject must be at least 28 weeks post-menstrual age and up to 52 weeks chronological age at enrollment.
- 2) Subject weight must be at least 500 grams (17.6 ounces) at time of enrollment.
- 3) Clinically diagnosed with SBS requiring PN/IV secondary to surgical resection of the intestine.
- 4) After major surgical resection leading to SBS, the subject has maximally 70% of expected bowel length preserved or an ostomy in place such that  $\leq$  70% of the small bowel is available for absorption.
- 5) Subject can tolerate at least 10 mL/kg/day of EN for at least 7 days at time of enrollment.
- 6) At time of enrollment subject is on at least 70% of prescribed PN/IV and no more than 30% of enteral nutrition based on total caloric intake for at least 7 days prior to study entry.
- 7) Subject is randomized into the trial within 4 months from the surgical resection that has led to the diagnosis of SBS
- 8) Subject's parent(s) or legal guardian(s) provide written informed consent.
- 9) Subject's parent(s) or legal guardian(s) understand and are willing to comply with all study procedures and requirements.

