##### **4.1.14.2. Enteral Nutrition (EN) Intake**

EN intake will be obtained at screening, baseline, randomization, and at each study visit (as described in [Appendix B](#)). In case of an acute medical event during the study period the patient will be clinically stable before study visit occurs. The total volume and the caloric value of enteral nutrition administered will be recorded in each study visit. The daily total amount of EN

and caloric content will be entered into the CRF. For patients discharged home a diary will be provided to confirm prescribed EN and PN intake.

Solids intake information will be collected at the site level and reported by the investigator as part of enteral intake in the CRF.

Negligible amounts of breast milk/formula/solids intake that are only provided for stimulation of suck and swallow coordination and not used as part of the calculations for providing adequate caloric needs for growth will not be calculated as part of daily enteral intake.

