#### **8.4. SAMPLE SIZE**

The sample size is based on testing the superiority of the high dose of NTRA-9620 compared to placebo on the primary endpoints of percent change in %PN from baseline to time “t” (PC\_PN0-t) where “t” = 12 and 24 weeks. On the basis of historical data, the assumed reduction in PC\_PN0-t is 30% and 42% in placebo and NTRA- 9620, respectively, at both 12 and 24 weeks. A common within-group standard deviation of 20% has been assumed for both arms.

Given the above specifications, and based on the use of a two-sided, two-sample comparison of means at the alpha = 0.025 level of significance, a sample of 45 subjects per group would provide approximately 80% power to demonstrate superiority. Since some subjects may not complete the entire trial, an additional 10% of subjects will be enrolled per arm (50 subjects per arm) to account for this potential loss. Thus, the proposed sample size is 150 subjects.

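### Secondary endpoints (k) and (l) divide by a baseline %EN that the entry criteria keep small and variable, so they lose precision that a change in percentage points would keep

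*Combined protocol and SAP*

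**What the plan says.** Section 8.3.4 lists among the other secondary endpoints (k) "Percent change from baseline in %EN based on total calories". Endpoint (l) is the volume counterpart, given in section 3.4.2.2 as "Percent change from baseline in %EN based on total volume". The synopsis lists the same pair. No formula is written out for %EN; I read it as 100 × (%EN at time t − baseline %EN) / baseline %EN. No absolute change in %EN appears in any endpoint list.

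Section 3.4.4 bounds the baseline on both sides. The lower bound is "Subject can tolerate at least 10 mL/kg/day of EN for at least 7 days at time of enrollment". The upper bound is "no more than 30% of enteral nutrition based on total caloric intake for at least 7 days prior to study entry".

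Section 8.5.5.3 leaves the analysis of the other secondary endpoints to the SAP, so no test, transformation, baseline adjustment or significance level is stated for (k) or (l).

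**The concern.** A percent change suits %PN, because an eligible infant starts at about 70% or more and the divisor is large and fairly stable. The same metric applied to %EN divides by a quantity that entry limits to at most 30% of calories and that may be only a few percent. Infants with similar enteral gains then get very different scores, and those with the lowest baselines supply most of the variance.

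Section 1.1 names enhancement of EN intake, alongside faster reduction of %PN, as the way to judge progress towards enteral autonomy. Endpoints (k) and (l) are the only listed efficacy endpoints expressed as %EN. If they are noisy by construction, a real enteral gain may go undetected in the only measures aimed directly at it.

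**Working it through.** **1. The plan's own figure.** Section 8.4 assumes that the reduction in %PN "is 30% and 42% in placebo and" NTRA-9620 respectively, with SD 20%. It claims about 80% power with 45 per group at two-sided 0.025. By the normal approximation the standardised distance is 12 / (20 × √(2/45)) = 2.85.
- Two-sided 0.025: power = Φ(2.85 − 2.24) = 73%.
- Two-sided 0.05: power = Φ(2.85 − 1.96) = 81%.

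The claimed 80% is reproduced only at two-sided 0.05. That is a separate matter. I use 0.05 below because 45 per arm then gives the planned power and the metrics can be compared from that starting point. The plan sets no level for (k) or (l).

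**2. How small the baseline can be.** The documents give no energy density, total energy or total volume, so these are assumptions.
- Calories, at 0.6–1.0 kcal/mL and 80–120 kcal/kg/day: 10 mL/kg/day is between 10 × 0.6 / 120 = 5% and 10 × 1.0 / 80 = 12.5%.
- Volume, at 100–180 mL/kg/day in total: between 10/180 = 5.6% and 10/100 = 10%.

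**3. Effect on one infant's score.** Assume EN + PN = 100% of calories. Let E be baseline %EN and r the fractional reduction in %PN.
- Change in points = (100 − E) × r
- Percent change = 100 × r × (100 − E) / E

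For the same 30% reduction in %PN (r = 0.30):

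| Baseline %EN | Change, points | Percent change |
|---|---|---|
| 30 | 21.0 | +70% |
| 20 | 24.0 | +120% |
| 10 | 27.0 | +270% |
| 7 | 27.9 | +399% |
| 5 | 28.5 | +570% |

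From top to bottom, the score in points rises by a factor of 28.5/21 = 1.4 and the percent change by 570/70 = 8.1.

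**4. Effect on power.** Simulation with 45 per arm and 3,000 trials per scenario. The reduction in %PN is normal with mean 30 or 42 and SD 20, capped at 100. Baseline %EN is uniform over the range shown. Tests are at two-sided 0.05. Efficiency is the squared ratio of the standardised differences (percent change over points). The last column is the share of within-arm variance of the percent change carried by the quarter of infants with the lowest baseline; it is 26% when all baselines are equal.

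| Baseline %EN | Points, t test | Percent, t test | Percent, ANCOVA on baseline | Percent, Mann-Whitney | Efficiency | Variance share |
|---|---|---|---|---|---|---|
| 15–30 | 81% | 71% | 79% | 71% | 0.79 | 45% |
| 10–30 | 79% | 58% | 73% | 61% | 0.61 | 56% |
| 7–30 | 78% | 49% | 66% | 56% | 0.48 | 63% |
| 5–30 | 79% | 38% | 57% | 50% | 0.37 | 69% |

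Repeat runs moved the unadjusted percent-change figures by up to 3 points (41%, 49%, 59% and 70% for floors of 5%, 7%, 10% and 15%). Using the reciprocal of baseline as the covariate raised the adjusted figure at the 5% floor to 66%. Log-uniform baselines gave similar unadjusted losses: 52% for 7–30 and 44% for 5–30. At efficiency 0.48, 45 infants per arm work like 45 × 0.48 ≈ 22.

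**The case against.** **The analysis is still open.** The SAP is to be written while the study is blind and prevails over the protocol (section 8.1). It could adjust for baseline, and section 8.5.1 already promises medians and percentiles. This stands in part: a reader might take the roughly 40% as the power of the planned analysis, but it belongs to an unadjusted t test that the documents do not specify. Adjustment recovers much of the loss. It does not cure it unless baselines stay well above the floor, because the protocol itself fixes the ratio in three places.

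**The baseline distribution is unknown.** This stands. With baselines of 15–30% an unadjusted analysis loses about 20% of efficiency, and an adjusted one loses little power. The calculation also treats %EN as the complement of %PN. The primary %PN instead uses Schofield requirements as its denominator (section 8.3.2), so the two need not sum to 100%. A 3% floor should not be used, since it lies below the 5–12.5% that the entry minimum implies.

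**Endpoint (l) was not simulated.** Correct. The 30% cap is on calories and bears on volume only indirectly.

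**The stakes are modest.** Also correct. These are 2 of 17 other secondary endpoints. Section 8.1.2 limits Type I error protection to the primary and key secondary endpoints, and (a) to (h) cover much of the same clinical question through PN.

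**Two stronger readings are not supported.**
- Section 4.1.14.2 says that "Negligible amounts of breast milk/formula/solids intake that are only provided for stimulation of suck and swallow coordination", and not used in the caloric calculations, "will not be calculated as part of daily enteral intake". A reader might infer zero baselines and an undefined endpoint. But eligibility requires at least 10 mL/kg/day tolerated for at least 7 days and baseline spans at least 7 days, so a single zero day does not make a zero baseline.
- A reader might infer that the endpoint would point the wrong way or mainly reflect chance imbalance. In simulation the arm difference had the wrong sign in about 4% of trials with a 5% floor, 1.5% with 10% and 0.7% with 15%. A significant result in the wrong direction occurred in 0.03% or fewer. The cost is precision, not misdirection.

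**Conclusion.** The point holds as a loss of precision in two non-key secondary endpoints. Percent change in %EN gives most weight to infants near the 10 mL/kg/day floor. Under the assumptions above, power falls from about 80% on percentage points to about 40–70% unadjusted, or about 60–78% adjusted for baseline, as the lowest baseline goes from 5% to 15%. The direction was the same in every scenario in which baselines varied; the size depends on a baseline distribution that the documents do not give. For (l) the mechanism is plausible but unquantified. The co-primary and key secondary conclusions are not affected. The change is worth making because it is cheap and these are the plan's only endpoints expressed as %EN.

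**What to change.** In the synopsis, section 3.4.2.2 and section 8.3.4, redefine (k) and (l) as the absolute change from baseline in %EN, in percentage points, by calories and by volume. Use the primary endpoint's 7-day averages (Days 78 to 84 and 162 to 168) and adjust for baseline %EN, for example by ANCOVA. Percent change may stay as a descriptive summary reported with medians. State the same in the SAP.

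The cost is wording. Daily EN and PN amounts are already recorded (sections 4.1.14.1 and 4.1.14.2), so no new data, visits or patients are needed.
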